and labeled with the same ID and kept together with the device package. The devices will be stored in a locked room in the division of gastroenterology. The kits will be transported by a research coordinator to the TRU on the day needed. The remaining kits will be stored in the a locked room in the GI clinic, labeled with the patient's ID. Only research coordinators within the division of gastroenterology will have access to the storage room. To track use and proper disposal of the devices, subjects will be asked to return the used device the following week (at time of the next stimulator placement or follow-up visit 5 if week 4). The doctor or research coordinator will record that device was returned and dispose it properly. The research coordinator will log this data every week on each subject as devices are returned.

Data Acquisition and Analysis

Data acquisition: we will collect EKG tracing to analyze HRV, which will include heart rate, high frequency HRV, low frequency HRV and RMSSD.

For the mitochondrial bioenergetics, we will collect basal respiration, ATP production, maximal respiration, spare respiratory capacity and extracellular respiration.

We will collect cytokines at baseline, week 4 and at visit 5

Statistical Analysis

Data Management

The data gathered will be entered into REDCap data system with each ID having a unique identifier for each participant. REDCap is a secure, web-based application for building and managing online databases. All data will be de-identified and samples will only have a unique identifier that will link the unique identifier with the patient's name.

The REDCap clinical database will be maintained by the Department of Quantitative Health Sciences, at the Children's Research Institute under the direction of [name].

EKG Data, questionnaire responses, and demographic data collection forms will be coded by a member of the research team so that all protected health information is removed. This coded data will not contain any visit dates. This coded data will be analyzed by collaborators [name]. (Ohio State University) and [name] Ph.D. (University of California, Irvine) who will not be privy to any PHI. Coded data will be shared via Onedrive. Each subject's identifying number and related electronic data will be kept on a secured, MCW password-protected database that provides access only to the PI and research staff.

Missing Data Handling

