Missing Data: Every effort will be made to avoid missing data. Using logistic regression, the pattern of missing data will be explored. Assuming the data are missing at random (MAR) multiple imputations for items will be used. Data analysis overview: Summary statistics, such as mean, median, standard deviation, range and correlation will be used as a first step to examine data. To satisfy parametric assumptions, we may perform transformations with justifications if possible and otherwise use non-parametric tests. We will use CART and biological and physiological information to identify interactions when formulating regression models. Statistical software employed for data analysis will be: Cytel StatXact, SAS version 9.4, Salford System CART for trees, SPSS Version 24. The power calculation was made using PASS 13.

Power

This is not applicable due to this being an exploratory pilot study. This study will be supported by a \$12000 from CTSI (if approved), and number of subject was based on budget.

We will similarly analyze the change in vagal tone at visit 1, visit 4 and visit 5 and the different variables of mitochondrial bioenergetics including basal respiration, ATP production, maximal respiration, spare respiratory capacity and extracellular respiration.

We will also compare cytokines at visit 1; 4 and 5 and if possible correlate the change in cytokines to changes in hfHRV and RMSSD.

J. PROVISIONS FOR MONITORING DATA TO ENSURE THE SAFETY OF SUBJECTS; AND ADDITIONAL SAFEGUARDS TO PROTECT THE RIGHTS AND WELFARE OF SUBJECTS WHO ARE LIKELY TO BE VULNERABLE

The PI will monitor the health of all patients in the study per standard clinical practice. The PI will monitor protocol adherence and supervise data collection, entry, and analysis.

K. ANTICIPATED BENEFITS ASSOCIATED WITH THE PROTOCOL TO HUMAN RESEARCH PARTICIPANTS AND SOCIETY

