the participant remains in the study for purposes of data collection for outcomes only a separate “Age of Majority” informed consent will be obtained.

O. PROCEDURES TO BE EMPLOYED IN ANALYZING DATA AND THE ANTICIPATED SIGNIFICANCE OF THE PROPOSED STUDY

Analyses will be conducted with SPSS and SAS software programs. Probability levels of < .05 will be used as cut offs for statistical significance.

The key significance of this study is the identification of a reduction in inflammatory cytokines, and increase in hfHRV. With this study, we hope to lay the foundation for the application of AED for pediatric functional GI disorders by demonstrating improvement in mitochondrial bioenergetics and reduction in inflammation as part of the pathophysiology. This is an innovative and novel understanding of the pathophysiology of FGID, which will enhance our knowledge on the brain-gut neural connectivity underlying functional disorders and ultimately improve patient care.

P. FINANCIAL RELATIONSHIPS

The EAD devices will be supplied by the distributing company (IHS) at manufacturing rate. A grant from Advancing a Healthier Wisconsin (AHW) will partially support this proposal and a CTIS Start Up Pilot award (\$12000) funding decision is pending. Patients will receive a stipend of \$20 at each of the following visits: Visit 1, Visit 4 and Visit 5. (After each blood draw is completed)

Q. ADVERTISEMENTS / FLIERS

Not applicable.

R. BIBLIOGRAPHY

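### A 7-subject study labelled exploratory still applies a p<.05 significance label, with no adjustment stated, to five unranked mitochondrial variables at three visits, and plans CART-guided interaction models

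*Combined protocol and SAP*

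**What the plan says.** Section D (Study Population) enrols 7 adolescents in one group. Under Power, the number is attributed to the budget, and of power itself the text says "This is not applicable due to this being an exploratory pilot study".

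Data Acquisition and Analysis lists five mitochondrial measures: "basal respiration, ATP production, maximal respiration, spare respiratory capacity and extracellular respiration". The text after Power says "We will similarly analyze the change in vagal tone at visit 1, visit 4 and visit 5 and the different variables of mitochondrial bioenergetics" and "We will also compare cytokines at visit 1; 4 and 5". It does not say which visits are contrasted, which variable or cytokine leads, or how many cytokines there are.

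The data analysis overview leaves scale and test open ("we may perform transformations with justifications if possible and otherwise use non-parametric tests") and adds "We will use CART and biological and physiological information to identify interactions when formulating regression models".

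Section O sets the only decision rule: "Probability levels of < .05 will be used as cut offs for statistical significance". It does not mention adjustment and does not call p-values descriptive. The same section hopes to lay a foundation for the device by "demonstrating improvement in mitochondrial bioenergetics and reduction in inflammation as part of the pathophysiology".

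The one ranking in the plan is in the Heart Rate Variability section, where RMSSD is the primary HRV outcome. Recordings are made both supine and standing, and the plan does not say which posture that outcome uses.

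**The concern.** The exploratory label is used to set aside a power calculation, while a significance threshold is kept for the results. Section B aims at better mitochondrial function and less inflammation. If any of several unranked variables at any of several visits can be called significant, a nominal success is more likely by chance than 5% suggests. The variable, visit, scale and test to stress can also be chosen after the data are seen. A later study might then be built on a mitochondrial effect that is noise. Separately, a tree search for interactions in 7 subjects will produce structure whether or not any exists.

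**Working it through.** The plan states no effect size, SD or error rate for the mitochondrial outcomes, so there is no figure of its own to reproduce.

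**Inputs from the plan.** n = 7; five mitochondrial variables; three visits; cut-off 0.05.

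**Assumptions, because the plan is silent.** Two-sided tests; 1, 2 or 3 visit contrasts per variable; correlation between the five variables from 0 to 0.9; normal data with equal correlations and independent visit noise; no true change. Cytokine, HRV and FDI tests are not counted.

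**Step 1: hand check.** For one contrast and independent variables, 1 - 0.95^5 = 22.6%.

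**Step 2: simulation.** 40,000 null data sets; chance of at least one two-sided p<.05 among the mitochondrial variables, from correlation 0.9 to correlation 0:

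| Test and complete subjects | 1 contrast | 2 contrasts | 3 contrasts |
|---|---|---|---|
| Paired t, n=7 | 11-23% | 20-38% | 27-50% |
| Paired t, n=5 or 6 | 12-23% | 21-39% | 28-51% |
| Exact signed-rank, n=7 | 11-21% | 20-37% | 27-48% |
| Exact signed-rank, n=6 | 8.5-15% | 16-27% | 22-36% |
| Exact signed-rank, n=5 | 0% | 0% | 0% |

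One overall repeated-measures test per variable at n=7 gives 11-22%, in effect the 1-contrast row. Against the nominal 5%, the 1-contrast paired-t result is 11.1/5 = 2.2 to 22.6/5 = 4.5 times as large.

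**Step 3: why the signed-rank rows fall.** The smallest two-sided p is 2/2^n: 0.0156 at n=7, 0.031 at n=6 and 0.0625 at n=5. The largest attainable level below 0.05 is 0.0469 at n=7 and 0.031 at n=6. At n=5 there is none.

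**Step 4: what a single comparison can do.** For a two-sided paired t-test at 0.05 with n=7 (noncentral t), power is 43% for a change of 0.8 SD, 60% for 1.0 SD and 80% for about 1.27 SD, where SD is that of the change. The 95% interval half-width is t(0.975, n-1)/sqrt(n): 2.447/2.646 = 0.92 SD at n=7, 1.05 at n=6 and 1.24 at n=5.

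**Step 5: interaction models.** The plan does not define the regression unit. As an illustration with one row per subject, an intercept, two predictors and their interaction use 4 parameters, leaving 7 - 4 = 3 residual degrees of freedom before any search by CART is counted. One row per visit gives more rows but still only 7 independent subjects.

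**The case against.** The strongest reply is that a pilot need not control familywise error, and that the plan already calls itself exploratory. That stands: the absence of adjustment is not the defect. The defect is keeping a significance label alongside that status. The language about demonstrating improvement is an aspiration, not a decision rule, and no weight is put on it beyond that. Adjustment is also not stated rather than expressly refused.

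Second, the contrasts are assumed. The wording could be met by one repeated-measures test per variable, and the hypothesis in Section B points towards a single before-and-after comparison. The five variables also belong to one set of bioenergetic measurements and are probably correlated. A reader might infer a false-positive chance near 50%; the documents do not support that as the headline. It needs three contrasts and uncorrelated variables.

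Third, a reader might infer that the chance is at least double the nominal level whatever is done. That is not so. The plan allows non-parametric tests, and with the signed-rank test the lower end at n=6 is 8.5%, or 1.7 times nominal. At n=5 the test cannot reject at all.

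Fourth, CART could be kept as hypothesis-generating, and the plan specifies no interaction test. The degrees-of-freedom example is only an illustration. That 7 subjects cannot support such interactions is a judgement from sample size, though it does not depend on the particular model.

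Finally, Section O speaks of hfHRV while RMSSD is the primary HRV outcome. This might be read as a conflict of endpoints. Section O is describing anticipated significance, and the plan treats both as vagal indices, so only the missing posture is a real gap.

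**Conclusion.** The point holds as a mismatch between exploratory status and a significance label. With 7 complete subjects and one test per variable, the chance of at least one false mitochondrial finding is about 11-23%, roughly two to four and a half times the stated cut-off. The 20-38% and 27-50% ranges are outer bounds for two and three contrasts. All of these depend on the assumed correlation and number of contrasts. They hold closely for the paired t-test at 5 to 7 subjects and for the signed-rank test at 7, but not for the signed-rank test with fewer. Counting cytokines, HRV indices and FDI would add further opportunities for a chance finding. The CART-guided interactions cannot be reported reliably from this sample. The trial's conduct is unaffected; what should change is how its results may be described.

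**What to change.** Make these changes before data are seen.

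1. **Preferred.** State in Section O that all results are exploratory and remove the p<.05 significance label. Report every variable and visit as paired change with an unadjusted 95% interval. Say explicitly that an interval excluding zero is not a claim of effect. This matters because a t-based interval excludes zero exactly when the paired-t p is below .05, so intervals alone would carry the same false-positive chance.
2. **If a significance claim is wanted.** Name one mitochondrial variable, one visit contrast, one scale and one test as the single primary comparison, and make inflammation exploratory. State the 80%-power figure of about 1.27 SD for a paired t-test at n=7, and that a signed-rank test cannot reach 0.05 with 5 subjects. Do not split alpha across two comparisons with a signed-rank test: 0.025 is out of reach with 6 subjects, where the smallest p is 0.031.
3. Delete the CART and interaction modelling from the data analysis overview.
4. Minor: state whether the primary HRV outcome is supine or standing RMSSD.

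The cost is wording in three places: the Heart Rate Variability section, the data analysis overview and Section O. No subjects, visits or assays are added. The downsides are that nothing beyond a single named primary, if there is one, can be called significant, and that one exploratory analysis is lost.
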